#### 4.1.2.1.2 Other Endpoints

- Landmark RFS by year: The Kaplan-Meier (K-M) estimate of RFS rate at 1 year, 2 years, 3 years, and 5 years
- Rate of histopathology tumor-free margin (R0) surgical resection
- Rate of pathological complete response (pCR) (Arm 1 only)
- Local recurrence-free survival (LRFS): Time from randomization to the earlier date of the first of local disease recurrence or death due to any cause. Local recurrence is defined as histologically or cytologically confirmed reappearance of melanoma in the area of up to 2 cm from the scar from the surgical excision or at the edge of the skin graft if that was used for closure. For subjects not having experienced an event by the cutoff date, LRFS will be censored at the last valid tumor evaluation before the data cutoff date. An event will be imputed at randomization for subjects who do not have an R0 surgical outcome. Subjects with a non-melanoma tumor identified at surgery will be censored at the day after randomization. **Sensitivity analyses as per RFS Sensitivity #1 (see Section 4.1.1) will be performed for LRFS.**
- Regional recurrence-free survival (RRFS): Time from randomization to the date of the first of regional disease recurrence or death due to any cause. Regional recurrence excludes local recurrence and is defined as histologically, cytologically, or radiographically confirmed reappearance of melanoma in the regional lymph node basin. New in-transit melanoma metastases in the regional lymphatic drainage will be reported as regional recurrence. Histological or cytological confirmation of new in-transit metastases is recommended but is not required. For subjects not having experienced an event by the cutoff date, RRFS will be censored at the last valid tumor evaluation before the data cutoff date. Subjects with a non-melanoma tumor identified at surgery will be censored a day after randomization. **Sensitivity analyses as per RFS Sensitivity #1 (see Section 4.1.1) will be performed for RRFS.**

- Distant metastases free survival (DMFS): Time from randomization to the earlier date of the first of distant metastases or death due to any cause. Distant metastases exclude local and regional recurrence and will include distant cutaneous/subcutaneous metastases, distant nodal metastases, or visceral, central nervous system, brain, or bone metastases. For subjects not having experienced an event by the cutoff date, DMFS will be censored at the last valid tumor evaluation before the data cutoff date. Subjects with a non-melanoma tumor identified at surgery will be censored at the day after randomization. Sensitivity analyses **as per RFS Sensitivity #1 (see Section 4.1.1) will be performed for DMFS.**
- Overall survival (OS): Time from randomization to death due to any cause
- Landmark OS by year: The Kaplan-Meier (K-M) estimate of the overall survival rate at 1 year, 2 years, 3 years and 5 years.

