7.2.4 Long-term Follow-up

All randomized subjects will be contacted by telephone, or clinic visit, to assess survival status, collect adverse events deemed by the investigator to be potentially related to talimogene laherparepvec (Arm 1 only), and, if applicable, commencement of any subsequent anticancer melanoma therapy. Follow-up will occur every 3 months (± 30 days) for 3 years following the safety follow-up visit and then every 6 months (± 30 days) until death, subject withdraws full consent, or up to 5 years after the last subject is randomized, which is first.

Radiographic tumor imaging, clinical tumor assessments, and tumor response assessments, will be performed as documented in [Section 7.2.2](#) every 3 months (± 30 days) for 3 years following the safety follow-up visit and then every 6 months (± 30 days) until distant disease recurrence, death, subject withdraws full consent, or up to 5 years after the last subject is randomized, whichever is first. Local and regional recurrences will be reported until appearance of distant recurrence, or end of study, whichever is first. Local recurrence is defined as histologically or cytologically confirmed reappearance of melanoma in the area of up to 2 cm from the scar from the surgical

excision or at the edge of the skin graft if that was used for closure. Regional recurrence (excludes local recurrence) is defined as histologically, cytologically, or radiographically confirmed reappearance of melanoma in the regional lymph node basin. New in-transit melanoma metastases in the regional lymphatic drainage will be reported as regional recurrence. Histological or cytological confirmation of new in-transit metastases is recommended but is not required. Distant metastases exclude local and regional recurrence and will include distant cutaneous/subcutaneous metastases, distant nodal metastases, or visceral, central nervous system, brain, or bone metastases.

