### 10.5.2 Analyses of Secondary Efficacy Endpoint(s)

KM estimates will be calculated for RFS, LRFS, RRFS, DMFS, RFS landmarks by year, OS landmarks by year and quartiles. Greenwood's formula ([Kalbfleisch and Prentice, 1980](#)) for standard error will be used to calculate CIs for each group and between-group differences in landmark KM rate estimates. CIs for quartiles of each group will be estimated per Brookmeyer and Crowley ([Brookmeyer and Crowley, 1982](#)) using a

log-log transformation and bootstrap methods will be used to estimate CIs for between-group differences (see [Section B.3](#) for SAS code fragments). For each group the equal-precision band method will be used to calculate a simultaneous confidence band for RFS, LRFS, RRFS and DMFS over the interval from 1 to 5 years ([Nair, 1984](#)) (see [Section B.2](#) for SAS code fragments).

An overall between-group difference in LRFS, RRFS, DMFS, and OS will be evaluated with a log-rank test and corresponding proportional hazard model with or without stratification by the two randomization factors.

Informative censoring due to distant recurrence is expected for LRFS. For LRFS, after considering distant recurrence as competing event, Gray's test ([Gray, 1988](#)) will be performed to assess the equality of cumulative incidence functions between treatment groups, and the subdistribution proportional hazards model ([Fine and Gray, 1999](#)) will be used to calculate treatment HR with 95% CI with or without stratification by the randomization factors. The same sensitivity analysis will be performed for DMFS with censoring considered a competing risk if the subject has a primary reason for ending the study after a local or regional recurrence withdrawal of consent or lost to follow-up. The same analysis will be performed for RRFS with censoring considered a competing risk if the subject has a primary reason for ending the study after a local recurrence of withdrawal of consent or lost to follow-up. Please see [Appendix B](#) for SAS code fragments.

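### LRFS and RRFS count deaths after distant recurrence but censor survivors back at their last tumor evaluation, so censoring depends on later survival; RRFS has no analysis with distant recurrence as the competing event

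*SAP*

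**What the plan says.** SAP 4.1.2.1.2 defines LRFS as "Time from randomization to the earlier date of the first of local disease recurrence or death due to any cause" and RRFS as "Time from randomization to the date of the first of regional disease recurrence or death due to any cause". Neither definition limits how long after the last scan a death may count. Subjects without an event are handled by "LRFS will be censored at the last valid tumor evaluation before the data cutoff date" and "RRFS will be censored at the last valid tumor evaluation before the data cutoff date".

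Protocol 7.2.4 runs imaging and clinical tumor assessment "until distant disease recurrence, death, subject withdraws full consent" or the end of follow-up. On the recurrence events it says "Local and regional recurrences will be reported until appearance of distant recurrence, or end of study, whichever is first". Survival follow-up does not stop there: "All randomized subjects will be contacted by telephone, or clinic visit, to assess survival status", until death, withdrawal of full consent, or 5 years after the last randomization.

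SAP 10.5.2 acknowledges that "Informative censoring due to distant recurrence is expected for LRFS". It adds Gray's test and a Fine-Gray model for LRFS, with distant recurrence as the competing event. For RRFS, the competing event is instead withdrawal of consent or loss to follow-up after a local recurrence.

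**The concern.** Take two subjects with distant recurrence on the same day. The one who dies before the data cutoff stays in the LRFS risk set until death and is an event. The one still alive is censored at the last tumor evaluation, at about the date of distant recurrence. After distant recurrence, the risk set therefore holds only subjects who will die before the cutoff. Kaplan-Meier, log-rank and Cox methods all assume that leaving the risk set carries no information about the later event; here it is determined by that event. RRFS has the same structure.

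No other planned analysis repairs this:

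- RFS Sensitivity #2 (the 90-day late-death rule) is written for RFS and applies only where no recurrence was documented.
- Sensitivity #1, which LRFS and RRFS do inherit, concerns surgical outcome.
- The inverse-probability-weighted analyses in SAP 10.5.2 address adjuvant therapy.

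At stake are the LRFS and RRFS landmark rates, their 80% intervals and, under some conditions, the hazard ratios. The trial's stated purpose is estimation.

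**Working it through.** **The plan's own figure.** The documents give no design figure for LRFS or RRFS. The RFS design table reproduces: at HR 0.70 with 64 events, the probability that the 80% interval lies below 1 is Φ(√64/2 × |ln 0.70| − 1.2816) = Φ(1.427 − 1.282) = 0.558, against 0.56 stated. That table is not in dispute.

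**Inputs.** From the documents: accrual of about 18 months (Protocol 3.5.1), cuts about 2, 3 and 5 years after the end of randomization, and 10% drop-out by the primary analysis. Assumed, because the documents do not give them: yearly hazards of 0.06 for local recurrence, 0.13 for distant recurrence, 0.01 for other death and 0.44 for death after distant recurrence. The last is ln 2 / (18.9/12), from the 18.9-month control-arm median of the phase 3 study described in Protocol 2.2, used as a proxy.

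**Target value.** With no recorded local recurrence after distant recurrence, the probability of being free of the recorded composite at time t is

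S(t) = e^(−0.20t) + [0.13/(0.44 − 0.20)] × (e^(−0.20t) − e^(−0.44t)).

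- 2 years: 0.670 + 0.542 × (0.670 − 0.415) = 0.809
- 3 years: 0.549 + 0.542 × (0.549 − 0.267) = 0.701
- 5 years: 0.368 + 0.542 × (0.368 − 0.111) = 0.507

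**Simulated Kaplan-Meier LRFS** (300,000 to 400,000 subjects). Only the censoring date of subjects alive after distant recurrence changes between columns.

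| Landmark and data cut | SAP rule | Last known alive | Shift (points) |
|---|---|---|---|
| 2 years, primary | 79.8% | 80.9% | 1.1 |
| 3 years, primary | 67.3% | 70.2% | 2.9 |
| 3 years, 3-year analysis | 68.2% | 70.2% | 2.0 |
| 5 years, final | 47.8% | 50.8% | 3.0 |

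The last-known-alive column agrees with the formula. At the final analysis the 2-year and 3-year shifts fall to about 0.4 and 0.9 points.

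**Range.** A second set of simulations was anchored on a 2-year RFS of 0.60. It assumed that 40 to 60% of recurrences are distant and 25% occur at the endpoint site, with death after distant recurrence at 0.231 to 0.90 per year and other death at 0.02 per year. Imputed events for non-R0 surgery were left out. The downward shift was 0.4 to 1.7 points at 2 years and 1.3 to 4.7 at 3 years (primary cut), and 0.6 to 6.4 at 5 years (final cut). At the primary cut, 7 to 20% of subjects were alive after distant recurrence.

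In the central case (50% distant, hazard 0.478 = −ln 0.62, from the 1-year stage IVM1a survival in Protocol 2.1), the 3-year rate at the primary cut was 64.2% under the SAP rule and 67.2% with the changed censoring, against a true 68.7%. The remaining 1.5 points come from the scan-to-cutoff gap in subjects without distant recurrence and are not part of the shifts above.

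**Hazard ratio for LRFS, primary cut, first set of rates.**

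| Assumed effect of Arm 1 | SAP rule | Last known alive |
|---|---|---|
| Distant recurrence halved, local unchanged | 0.78 | 0.81 |
| Local and distant both × 0.7 | 0.724 | 0.746 |
| Only local recurrence differs | 0.850 | 0.851 |

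In the first row the 3-year difference is 6.7 points under the SAP rule and 5.0 with consistent censoring.

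**The case against.** **Size.** The 3-year rate at the primary cut is the least favorable pairing. With 18 months of accrual and a cut 2 years after randomization ends, only (3.5 − 3)/1.5, or one third, of subjects can have 3 years of follow-up. The 2-year shift is about 1 point. With 75 subjects per arm and a rate near 70%, the 80% half-width is about 1.28 × √(0.7 × 0.3/75) = 7 points per arm and 10 points for the difference. These are secondary endpoints in a descriptive trial. All of this stands and limits the weight of the point. It does not justify censoring that depends on the outcome, and the 80% intervals do not reflect the error.

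**Direction.** A reader might infer that the rates are always too low. The documents do not support that, because local and regional recurrences after distant recurrence are not recorded. In the central case, if these occurred at twice the earlier rate, the 2-year rate at the primary cut would match the full composite (78.4% against 78.4%). At four times it would be about 1 point too high (78.4% against 77.4%). The downward direction therefore holds only against recorded recurrence or death.

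**Hazard ratio.** A reader might also infer that the rule favors Arm 1. That requires the treatment to reduce distant recurrence. Protocol 2.3 expects this, but it is not established, and when only local recurrence differs the ratio barely moves.

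**LRFS is already handled.** This is partly right: the SAP recognizes the problem. But Gray's test and the Fine-Gray model address a different quantity as a sensitivity analysis, and the LRFS Kaplan-Meier, log-rank and Cox results keep the rule. For RRFS the gap is complete.

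**Conclusion.** The point holds for both endpoints. The combined rules make censoring depend on later survival, and the Kaplan-Meier LRFS and RRFS rates are too low relative to recorded recurrence or death. Under the first set of assumed rates the shift is about 1 point at 2 years and 3 points at 3 years at the primary cut, about 2 points at 3 years at the planned 3-year analysis, and about 3 points at 5 years at the final analysis. The range of about 0.4 to 6.4 points reflects that the documents fix neither the share of recurrences that are distant nor survival after distant recurrence. Across the effect patterns and both cuts examined, the hazard ratio was about 0.02 to 0.04 lower under the SAP rule when Arm 1 had less distant recurrence, and almost unchanged when distant recurrence was equal.

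The documents do not support reading this as a fixed bias against the full composite, as a bias that always favors one arm, or as a threat to the primary RFS analysis. It is a correctable flaw in two secondary endpoints, and worth correcting before those results are reported.

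**What to change.** 1. In SAP 4.1.2.1.2, for the LRFS and RRFS Kaplan-Meier, log-rank and Cox analyses, censor subjects alive after distant recurrence at the date last known alive. State beside the rule that local or regional recurrences after distant recurrence are not recorded, so the result describes recorded recurrence or death and may be too high against the full composite.
2. In SAP 10.5.2 and Table 2, add RRFS to the planned Gray and subdistribution analysis with distant recurrence as the competing event.

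The cost is a small SAP rewording. Survival status is already collected, and the code in SAP Appendix B.8 and B.9 can be reused. The downside is that subjects after distant recurrence are treated as free of unrecorded local or regional recurrence. In the central case with those recurrences at four times the earlier rate, the changed rule gives 79.5% at 2 years at the primary cut, against 77.4% for the full composite: 2.1 points too high. Censoring everyone at distant recurrence and ignoring later deaths would also be symmetric, but it answers a different question (about 85% at 2 years in the central case).

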#### 4.1.2.2 Safety Endpoints

- Subject incidence of treatment-emergent and treatment-related adverse events
- The incidence of subjects with herpetic lesions found to be positive for talimogene laherparepvec DNA per qPCR in swab samples collected from lesions suspected to be herpetic in origin and the rate of positive lesions (if any); Potential or known unintended exposure to talimogene laherparepvec, related suspected signs or symptoms, and detection of talimogene laherparepvec in a subject's household member, caregiver, or healthcare provider

#### 4.1.3 Exploratory Endpoints

The following endpoints are included as exploratory endpoints and their analysis plan may be described in a separate supplemental SAP if appropriate and they may be reported separately from the primary CSR.

- Correlation between baseline intratumoral CD8+ cell density in melanoma lesions and clinical outcomes
- Correlation between changes in an intratumoral CD8+ cell density in melanoma lesions during talimogene laherparepvec treatment and clinical outcomes (for Arm 1 only)
- Correlation between the changes in the population of tumor-specific cytotoxic T-cells in blood samples during treatment and clinical outcomes (for Arm 1 only)
- Assessment of blood and tumor for potential biomarkers which correlate with or predict clinical outcomes to talimogene laherparepvec

#### 4.2 Planned Covariates

**The following covariates, including the stratification factors,** will be used, with possible exceptions where associated subgroups are too small (eg, < 20 subjects) or have too few events (< 5 events), to examine efficacy **individually and multivariately:**

- Region, if more than 10% subjects in ITT population are from non-USA countries (USA or non-USA)
- Age at baseline: < 50, ≥ 50; < 65, ≥ 65; < 75, ≥ 75 years

- Number of measurable tumors at baseline (**will be dichotomized based on the median**)
- The sum of the products of the two largest perpendicular diameters of baseline measurable lesions (SPD) (**will be dichotomized based on the median**)
- Baseline absolute lymphocyte count:  $\leq 1000$  vs  $> 1000$
- **Recurrent disease  $\geq 1$  year from primary diagnosis vs recurrent disease  $< 1$  year from primary diagnosis vs no prior melanoma**
- Current disease stage (IVRS): IIIB nodal vs IIIB in-transit vs IIC nodal vs IIIC in-transit with nodal vs IV M1a
- Baseline ECOG performance status: 0 vs 1
- BRAF mutation status: mutation present vs mutation not present
- Previous systemic anti-cancer therapy for melanoma: yes vs no
- Previous systemic immune check-point inhibitor therapy for melanoma: yes vs no
- **Planned adjuvant therapy (IVRS): adjuvant systemic therapy with or without radiotherapy vs radiotherapy without adjuvant systemic therapy vs none**

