### 10.5.1 Analyses of Primary Efficacy Endpoint(s)

An overall between-group difference in RFS will be evaluated with a log-rank test and corresponding proportional hazards model without stratification. Sensitivity analyses, using alternate definitions of RFS as defined in [section 4.1.1](#), will be evaluated in the same manner. Additionally, for RFS, a log-rank test and proportional hazards model with stratification by the two randomization factors will also be conducted.

A sensitivity analysis will be performed censoring RFS at the start of all or selected actual adjuvant therapy for melanoma. However, censoring at start of all or selected adjuvant therapy for melanoma may introduce dependent censoring as the ability to receive further adjuvant therapy will likely be correlated with RFS. An inverse probability censoring weighting (IPCW) method (Robins, et al) which may reduce the potential bias will also be used to obtain an estimate of the treatment effect on RFS and may include baseline covariates in [Section 4.2](#).

In order to assess the impact of imbalances in the type of adjuvant therapy, a **stratified** Cox model will be repeated stratifying actual adjuvant systemic therapy (yes vs no). A KM time to event plot for RFS will be generated by 4 groups (Arm 1 with adjuvant systemic therapy, Arm 1 without adjuvant systemic therapy, Arm 2 with adjuvant systemic therapy, Arm 2 without adjuvant systemic therapy), and 2 separate KM plots will be generated by randomized treatment group in subjects with and without adjuvant systemic therapy respectively. If warranted due to actual adjuvant therapy (eg, the planned adjuvant therapy stratification factor is discordant with the actual for > 10% of all subjects), the stratified Cox model analysis will be repeated stratifying on **actual** adjuvant therapy type (**adjuvant systemic therapy with or without radiotherapy vs radiotherapy without adjuvant systemic therapy vs none**).

**To explore the prognostic and/or predictive value of the covariates listed in [Section 4.2](#), univariate and multivariate proportional hazards models without stratification will be used. Subgroup analyses will be evaluated with a log-rank test and corresponding proportional hazards model without stratification.**

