A sensitivity analysis will be performed for LRFS censoring at the start of all or selected actual adjuvant therapy (systemic therapy radiotherapy) for melanoma. However, censoring at start of selected adjuvant therapy (systemic therapy radiotherapy) for melanoma may introduce dependent censoring as the ability to receive further adjuvant therapy will likely be correlated with LRFS. An inverse probability censoring weighting (IPCW) method (Robins, et al) which may reduce the potential bias will also be used to obtain an estimate of the treatment effect on LRFS and may include baseline covariates in [Section 4.2](#). Similar analyses will be performed on DMFS and RRFS.

If warranted due to actual adjuvant therapy (eg, the planned adjuvant therapy stratification factor is discordant with the actual for > 10% of all subjects), the stratified Cox model analysis will be repeated stratifying on **actual** adjuvant therapy type

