## B.10 IPCW

```
/*Model probability of not receiving all or selected actual adjuvant  
therapy for melanoma including time-independent covariate(s)*/  
proc logistic data=time_indep;
```

```
  class <categorical time-independent covariate(s)>;  
  model subther(event='0') = <time-independent covariate(s)>;  
  output out=out1 prob=num;  
run;
```

```
proc sort data = time_dep;  
  by descending subther;  
run;
```

```
/*Model probability of not receiving all or selected actual adjuvant  
therapy for melanoma including time-independent covariate(s) and time-  
dependent covariate(s)*/
```

```
proc genmod data = time_dep descending order=data;  
  class <categorical time-independent covariate(s)> <categorical time-  
dependent covariate(s)> usubjid;  
  model subther = <time-independent covariate(s)> <time-dependent  
covariate(s)> / d=binomial link=logit;  
  repeated subject=usubjid;  
  output out=out2 prob=den;  
run;
```

```
proc sort data=out1;by usubjid;run;  
proc sort data=out2;by usubjid;run;
```

```
/*Calculate weights*/  
data dat1;  
  merge out1 out2;  
  by usubjid;  
run;
```

```
data dat2;  
  set dat1;  
  by usubjid;  
  retain w_num w_den;  
  if first.usubjid then do;  
    w_num = 1;  
    w_den = 1;  
  end;  
  w_num = w_num*num;  
  w_den = w_den*den;  
  
  if subther = 1 then weights = (1-w_num)/(1-w_den);  
  else if subther = 0 then weights = w_num/w_denom;  
run;
```

---

```
data dat3;
  merge dat2(in=a) adam.adtte(in=b where=(paramcd='RFSI' keep=usubjid
paramcd aval cnsr);
  by usubjid;
  if a and b;
run;

/*HR and corresponding CI using IPCW*/
proc phreg data = dat3;
  class trt01p(ref="SURGERY");
  model aval*cnsr(1) = trt01p;
  freq weights / nottruncate;
  hazardratio trt01p / alpha=0.05 cl=wald diff=ref;
  strata <stratification factors>;
run;
```

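### Cutting tumor count and baseline tumor area at the median before they enter the exploratory RFS Cox models discards prognostic information without need

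*SAP*

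**What the plan says.** SAP Section 4.2 lists the covariates for examining efficacy, singly and jointly. It allows exceptions where subgroups are small or "have too few events (< 5 events), to examine efficacy". For number of measurable tumors and for SPD, the form is fixed: each "will be dichotomized based on the median". The SAP does not say on which side a value equal to the median falls.

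SAP Section 10.5.1 says of this list that "univariate and multivariate proportional hazards models without stratification will be used" to explore prognostic and predictive value. SAP Section 7.4 takes its efficacy subgroups from the same list.

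The inverse-probability-of-censoring-weighted (IPCW) sensitivity analyses are tied to the list only loosely. For RFS, the weighted estimate is of the "treatment effect on RFS and may include baseline covariates in" Section 4.2. For local recurrence-free survival, SAP Section 10.5.2 uses matching words, "treatment effect on LRFS and may include baseline covariates in" Section 4.2, and plans similar analyses for DMFS and RRFS. The code in SAP Appendix B.10 has placeholders and names no covariate.

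Protocol Section 10.1.3 lists both covariates without a cut point.

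**The concern.** Both covariates are collected in finer form than the models will use. Protocol Appendix D has lesions measured in two dimensions in millimeters, with the products summed. A median split treats a subject just above the median and one far above it as the same, and two subjects close together on either side of it as different.

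At stake is the precision of the prognostic and predictive estimates for tumor burden, and how well the multivariate model adjusts for burden when it assesses the other factors. A second, conditional issue is the weighting. If weights are built on the split, differences in burden within each half stay uncorrected when subjects are censored at the start of adjuvant therapy.

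**Working it through.** **The plan's own figure.** The documents state no figure for this loss, so the first check is whether Table 1 involves these covariates. First row: HR = ln(0.70)/ln(0.60) = 0.698. The 80% CI is 0.698 × exp(±1.2816 × 2/√64) = 0.507 to 0.962, against 0.51 to 0.96 stated. The row reproduces with neither covariate in the calculation. SAP Table 2 gives the primary analysis as an unstratified log-rank test and Cox model in the ITT set, again with neither.

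**Information lost by the split.** For a modest effect linear in X, and setting aside correlation with the other covariates, the fraction of information kept is the squared correlation between X and the indicator X > median. For a standard normal X, the covariance is 0.399 (the density at 0) and the SD of the indicator is 0.5. The correlation is 0.399/0.5 = 0.798, and its square is 0.637 = 2/pi. The loss is 1 - 0.637 = 36.3%.

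The documents give no distribution for either covariate, so other shapes were tried by simulation (2 million draws each; all shapes are assumptions):

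| Assumed shape, effect linear on the scale shown | Loss |
|---|---|
| Normal (e.g. log SPD) | 36% |
| Uniform | 25% |
| Exponential | 52% |
| Lognormal, raw scale, sigma 0.5 | 48% |
| Lognormal, raw scale, sigma 1 | 73% |
| Counts (several shapes, scales and tie rules) | 22% to 70% |

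**Ties in the count.** Two assumed distributions show the effect of the missing rule.
- One plus a Poisson(1) count has median 2. The high group holds 26% of subjects if the cut is > 2 and 63% if it is ≥ 2. The loss is 30% or 42%.
- A geometric count with parameter 0.6 has median 1. A cut at > 1 puts 40% in the high group. A cut at ≥ 1 puts everyone there, so there is no split.

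**IPCW, if these covariates are used there.** A randomized trial of 1,000,000 subjects per scenario was simulated, with control 2-year RFS 0.60 and HR 0.70. A normal covariate drove both the RFS hazard (log HR 0.3 to 0.5 per SD) and adjuvant start (log odds ratio 0.3 to 0.7 per SD), with baseline adjuvant use of 30%. These effect sizes, and arm interactions of up to 1.4 in absolute value, are assumptions.
- Where adjuvant start depended on burden equally in both arms, the bias in the log HR without covariate weighting was only -0.001 to -0.006.
- Where adjuvant use, or its dependence on burden, differed by arm, the bias without covariate weighting was 0.039 to 0.161 in absolute value. Split-based weights left 35% to 43% of it (0.014 to 0.057). Weights from the true continuous relation, a best case, left at most 0.004.
- For scale, the standard error of the log HR at 64 events is 2/√64 = 0.25, and 0.057/0.25 = 0.23 standard errors.

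**The case against.** The strongest reply is that the Section 4.2 list also defines the subgroups, for which a median split is a sensible device, and that what remains is a modeling preference in exploratory work. All analyses are descriptive, and SAP Table 2 says only that these Cox models may be used. That limits the importance of the point. It does not remove it: Section 10.5.1 says the models will be run, and Section 4.2 offers no other form for these two covariates.

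Several stronger readings are tempting, but the documents do not support them.
- **A reader might turn the 36% into events** (64 × 0.363 = 23 of 64). The 64 events time the primary RFS analysis, which uses neither covariate and loses nothing.
- **A reader might take about a third as the loss for both covariates.** That figure needs a normal covariate with a linear effect, and the tumor count is discrete.
- **A reader might say that the weighted analyses are left confounded by tumor burden.** Use of these covariates there is optional. Arms are randomized, and the stated problem is that censoring at adjuvant start "may introduce dependent censoring as the ability to receive further adjuvant therapy will likely be correlated with RFS". The risk is selection bias from dependent censoring, and it needs a difference between arms.
- **A reader might object that the cut is unknown until the data are in.** The rule is prespecified and uses baseline values only, so it cannot be tuned to outcome.
- **A reader might extend the point to the logistic models.** SAP Section 10.5.2 mentions only baseline factors there and does not cite Section 4.2.

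A caution about model size also stands. The list carries about 17 to 19 parameters, depending on how the age cuts are used, before treatment or interactions are added. That is 64/17 = 3.8 events per parameter or fewer, which argues against splines.

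**Conclusion.** The point holds as a minor, avoidable loss of efficiency in the exploratory RFS Cox models of SAP Section 10.5.1. The loss is 36% of a covariate's information if it is roughly normal with a linear effect, and about 22% to 73% across the other shapes tried. For the tumor count, the missing tie rule can also make the split very uneven or void.

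The effect on the IPCW analyses is conditional on three things: that these covariates are included, that they enter as splits, and that adjuvant start depends on burden differently by arm. The last is possible in an open-label trial with adjuvant therapy at the investigator's discretion, but the documents do not show it. Even then, the largest bias left by split-based weights in the scenarios tried was about a quarter of a standard error. No primary or landmark result changes.

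**What to change.** In SAP Section 4.2, keep the median split for subgroup displays only, and state how values equal to the median are assigned. In the Section 10.5.1 Cox models, enter log(SPD) and tumor count (or log count) as single continuous terms. Use the same form in the IPCW weight models if these covariates are included there.

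The cost is a few lines of SAP text. No new data are needed, and each continuous term uses one parameter, as the split does. The downsides are slightly less simple tabulation and an assumption of linearity on the chosen scale. The loss falls to zero only if that scale is about right. With about 64 events, splines are best avoided.
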